Following the first administration of Pan-HER in monkeys, Pan-HER showed a rapid clearance from serum with short half-lives (T½) ranging from 1 to 3 days over the dose levels tested. A trend of increasing half-life with increasing dose was observed.

Dose-limiting toxicities (DLTs) in the form of diarrhea, dehydration and weight loss as well as skin sores/lesions were recorded after the second infusion of Pan-HER at 24 mg/kg and after one infusion at 36 mg/kg. The toxicity profile and PK profile indicate target engagement and that the toxicity is exaggerated pharmacology reflecting the mode of action of Pan-HER.

In the pivotal toxicology study, once-weekly IV infusions of Pan-HER to cynomolgus monkeys for six weeks at dose levels of 15 mg/kg/week or below were tolerated with no adverse signs of toxicity. Microscopically, there were no systemic findings, but locally thrombus formation and intimal proliferation within the saphenous veins were observed, and an increase in the inflammatory response in and around the infusion sites. These findings are considered as secondary toxicity features related to nonclinical immunotoxicity and not a direct target mediated toxicity.

Tissue cross reactivity studies showed specific positive staining with Pan-HER in the majority of human and cynomolgus monkey tissues examined. Specific positive staining with Pan-HER was observed mainly in tissues with epithelial and/or endothelial components and/or in the connective tissue.

Confidential Page 26 of 156

An *in vitro* safety study (i.e., a human whole blood activation assay using blood from six healthy donors) indicated that Pan-HER has a low risk of triggering acute immune toxicity in human blood as no significant increase in cytokine release was observed.

In conclusion, data from toxicology, tissue cross reactivity, PK and the *in vitro* safety study in human whole blood indicate that Pan-HER can be safely tested in human cancer patients. Based on the data described in the pivotal study, the No Observed Adverse Event Level (NOAEL) is considered to be 15 mg/kg.

For further information, refer to the Investigator's Brochure.

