3.2.4 Summary of Clinical Findings

3.2.4.1 Protocol Sym013-01

This is the first clinical trial to study Pan-HER. As of Amendment 6, a total of 19 patients have been entered to Part 1 of this trial: 1 patient each at 1 mg/kg and 2 mg/kg weekly (Q1W), 4 patients at 4 mg/kg Q1W, 3 patients at 6 mg/kg every second week (Q2W), 7 patients at 9 mg/kg Q2W, and with Amendment 5, 3 patients at the recently initiated cohort of 9 mg/kg Q2W + mandatory intensive prophylaxis for infusion-related reactions (IRRs) and oropharyngeal mucositis. Adverse events (AEs) observed at the 4 mg/kg Q1W dose activated the stopping rule of the single-patient dose cohort titration and resulted in transition to a 3+3 trial design. Effective with Amendment 3, due to Grade 1-2 oral mucositis, rash, and diarrhea at the 4 mg/kg Q1W dose, the dosing interval in this trial was changed from Q1W to Q2W for doses of 6 mg/kg and higher. Overall, the most frequently occurring, treatment-related AEs have been IRRs, oral mucositis, rash, and diarrhea.

Regarding IRRs, despite required premedication with a glucocorticoid and an antihistamine, 2 of 4 patients at 4 mg/kg Q1W experienced Grade 1-2 events, and 2 of 3 patients at 6 mg/kg Q2W experienced Grade 2 events. Per protocol, the occurrence of 2 IRRs in the 6 mg/kg Q2W cohort resulted in prolongation of infusion from a minimum duration of 2 hours to 2.5 hours, beginning with the 9 mg/kg cohort. Two (2) of the first 4 patients at 9 mg/kg Q2W experienced Grade 1-2 IRRs, and a fifth patient experienced a Grade 3 IRR. The Grade 3 event met the protocol-specified DLT criteria and was reported as a study drug-related serious adverse event (SAE). The patient was discontinued from study and the 9 mg/kg Q2W cohort was expanded. In addition, the minimum duration of infusion for subsequent patients was once again extended, from 2.5 hours to 3 hours, and as allowed per protocol, additional premedications were recommended for all future patients, to include predosing with montelukast and oral

Confidential Page 27 of 156

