4.10.4 Pharmacokinetics

4.10.4.1 Pharmacokinetic Concentrations

Serum concentrations for each of the six monoclonal antibodies in Pan-HER will be listed by mAb, dose schedule, dose group, patient, actual time relative to dosing, scheduled time and time deviation from scheduled time. The unit for the concentrations will be $\mu\text{g/mL}$.

Patient profiles serum concentrations vs. time points for each mAb will be plotted by dose schedule and dose group.

The following definitions are used for PK plots and tables:

PAREXEL International
Statistical Analysis Plan Template for Early Phase Studies

Symphegen A/S

Sym013-01

- First profile for weekly: all PK points from Cycle 1 Day 1 to Cycle 1 Day 8 (pre-dose)
- 2nd profile for weekly (4th dose): all PK points from Cycle 1 Day 22 to Cycle 2 Day 1 (pre-dose)
- First profile for biweekly: all PK points from Cycle 1 Day 1 to Cycle 1 Day 15 (pre-dose)
- 2nd profile for biweekly (3rd dose): all PK points from Cycle 2 Days 1 to Cycle 2 Day-15 (pre-dose).
- Dosing/sampling occasions for weekly dosing: Week 1, 2, 3, 4, 5, 6 etc., EOT, 1MFUP
- Dosing/sampling occasions for biweekly dosing: Week 1, 3, 5, 7, 9 etc., EOT, 1MFUP
- Peaks: serum concentration for each mAb assessed at EOI for each dosing occasion
- Troughs: serum concentrations for each mAb assessed prior to SOI for each dosing occasion

Violations of scheduled sampling will be reviewed on a patient by patient basis by Symphegen and PAREXEL. Following data review by Symphegen's pharmacokinetic expert, data points may be excluded from mean calculations and parameter calculation based on the below criteria:

- Individual outlying data points which are markedly deviating from the preceding and following time points
- Data points or PK profiles which are not compatible with known physiological processes underlying the PK properties
- Unexpected events or protocol deviations documented in e.g. laboratory notes or in protocol deviation reviews

Exclusions will be documented in the study files and the PC/PP files.

Following plots will be produced:

PAREXEL International
Statistical Analysis Plan Template for Early Phase Studies

Symphogen A/S

Sym013-01

- One panel per mAb, Dose Schedule and Dose group combination showing a profile for each patient: Patient Profiles for concentration vs. Actual Time by Dose Schedule and Dose Group (peak and trough for each dosing occasion) – Linear

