The arithmetic and geometric means of the serum concentrations of each of the six mAbs vs. nominal time points will be plotted by dose group with +/-1 standard deviation (for arithmetic means). In figures of geometric means, error bars will be calculated using the following formula: $\text{Exp}(\text{mean_Ln} \pm \text{sd_Ln})$ where 'sd_Ln' denotes the standard deviation of the concentration values on the log base 10 scale and 'mean_Ln' denotes the arithmetic mean of the concentration values on the log base 10 scale.

The following mean concentration vs. time plots will be produced:

- Arithmetic Mean Concentration for each of the six mAbs vs. Planned Time Point by Dose Group and Dose Schedule (First and 2nd profiles) – Linear
- Geometric Mean Concentration for each of the six mAbs vs. Planned Time Point by Dose Group and Dose Schedule (First and 2nd profiles) – Semi-log
- Arithmetic Mean Peak and Trough Concentrations for each of the six mAbs vs. Planned Time Point by Dose Group and Dose Schedule (peaks and troughs at all dosing occasions) – Linear
- Geometric Mean Peak and Trough Concentrations for each of the six mAbs vs. Planned Time Point by Dose Group and Dose Schedule (peaks and troughs at all dosing occasions) – Semi-log

PAREXEL International
Statistical Analysis Plan Template for Early Phase Studies

Symphogen A/S
Sym013-01

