4.10.4.3 Pharmacokinetic Parameters

Pharmacokinetic parameters for the first and second PK profile (as defined in 4.10.4.1) for each patient and each monoclonal antibody will be derived by model-independent, non-compartmental analysis (NCA) according to Symphogen's local procedures.

All derived serum PK parameters will be listed by mAb, dose schedule, dose group, patient, and actual time point (Listing 16.2.6.2.1-2) and summarized descriptively by mAb, dose schedule and group and day (Table 14.2.2.1-2). The following descriptive statistics will be presented for PK parameters: n, arithmetic mean, SD, geometric mean, geometric CV% (calculated as: $gCV\% = \text{SQRT}(\exp(s^2) - 1) * 100$; where s is the standard deviation of the log-transformed values), median, minimum and maximum values.

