Figure 14.2.15 Geometric Mean Concentration vs. planned time for each of the six mAbs by Dose Group (First and 2nd profiles) – Semi-Log (Full Analysis Set) *

Figure 14.2.16 Arithmetic Mean Peak and Trough Concentrations for each of the six mAbs versus planned time point by Dose Group (peaks and troughs at all dosing occasions) – Linear (Full Analysis Set) *

Figure 14.2.17 Geometric Mean Peak and Trough Concentrations for each of the six mAbs versus planned time point by Dose Group (peaks and troughs at all dosing occasions) – Semi-Log (Full Analysis Set) *

Figure 14.2.18 Spaghetti Plot for Selected Hematology parameters (Full Analysis Set) *

Figure 14.2.19 Spaghetti Plot for Selected Biochemistry parameters (Full Analysis Set) *

Figure 14.2.20 Spaghetti Plot for Selected Coagulation parameters (Full Analysis Set) *

Figure 14.2.21 BoxPlot for Selected Hematology parameters by Visit (Full Analysis Set)

Figure 14.2.22 BoxPlot Plot for Selected Biochemistry parameters by Visit (Full Analysis Set)

Figure 14.2.23 BoxPlot Plot for Selected Coagulation parameters by Visit (Full Analysis Set)

PAREXEL International
Statistical Analysis Plan Template for Early Phase Studies

Symphogen A/S

Sym013-01

Figure 14.2.24 BoxPlot for Selected Hematology parameters by Visit and Tumor Type (Full Analysis Set)

Figure 14.2.25 BoxPlot Plot for Selected Biochemistry parameters by Visit and Tumor Type (Full Analysis Set)

Figure 14.2.26 BoxPlot Plot for Selected Coagulation parameters by Visit and Tumor Type (Full Analysis Set)

Figure 14.2.27 Waterfall Plot of the Best Percent Change from Baseline in Sum of Diameters of Target Lesions (Full Analysis Set) *

Figure 14.2.28 Waterfall Plot of the Best Percent Change from Baseline in Sum of Diameters of Target Lesions by Primary Tumor Type (Full Analysis Set) *

Figure 14.2.29 Kaplan Meier Survival Curve for Time To Progression (Full Analysis Set) *

Figure 14.2.30 Swimmer Plot of Duration of Treatment and Tumor Response (Full Analysis Set)
*

Listing 16.2.1.1 Patients Disposition (All Consented Patients) *

Listing 16.2.1.2 Screen Failure and Patients Not Meeting Eligibility Criteria (All Consented Patients) *

Listing 16.2.2.1 Protocol Deviations and Violations (All Consented Patients) *

Listing 16.2.3.1 Analysis Sets (All Consented Patients) *

Listing 16.2.4.1 Demographics and Baseline Characteristics (All Consented Patients) *

Listing 16.2.4.2 Medical and Surgical History (All Consented Patients) *

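### SAP 4.10.4.1 defines the geometric-mean error bars with Exp() but puts the mean and SD on the log base 10 scale; coded as defined, the bars in Figures 14.2.15 and 14.2.17 are wrong

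*SAP*

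**What the plan says.** SAP 4.10.4.1 (Pharmacokinetic Concentrations) plans plots of arithmetic and geometric mean concentrations against nominal time for each of the six antibodies. For the geometric means it states "In figures of geometric means, error bars will be calculated using the following formula" and gives Exp(mean_Ln ± sd_Ln). It then defines the two inputs:

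- `sd_Ln` "denotes the standard deviation of the concentration values on the log base 10 scale"
- `mean_Ln` "denotes the arithmetic mean of the concentration values on the log base 10 scale"

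The same section fixes the reporting unit as µg/mL.

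Two planned outputs use the rule. One is "Figure 14.2.15 Geometric Mean Concentration vs. planned time for each of the six mAbs by Dose Group" (first and second profiles). The other is Figure 14.2.17 (peaks and troughs at all dosing occasions). Both carry the asterisk in SAP section 6, so under SAP 4.14 they go into the abbreviated report.

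SAP 4.10.4.3 gives the geometric CV of PK parameters as SQRT(exp(s^2) − 1) × 100, "where s is the standard deviation of the log-transformed values". It does not name the base.

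**The concern.** Exp() gives back a concentration only if its argument is on the natural-log scale. The formula and the `_Ln` names point to natural logs, while the written definitions say base 10, twice. Nothing else in the SAP settles the conflict.

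The PK profile is a secondary objective. SAP 4.14 drops the summed Pan-HER concentration because the six antibodies were found not to behave alike. The per-antibody mean figures therefore carry the visual comparison between antibodies and dose groups. Bars that are too short and in the wrong place would mislead on spread, in cohorts that are already small.

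**Working it through.** **Inputs.** The formula and the two definitions are from SAP 4.10.4.1. The documents give no observed geometric mean or SD for any antibody, so every concentration and SD below is assumed. The SAP states no numerical bar, so there is no figure to reproduce.

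**Algebra.** Let G be the true geometric mean, s the natural-log SD, and k = 1/ln(10) = 0.4343.

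- On the log10 scale the mean is k·ln(G) and the SD is k·s.
- Correct limits: exp(ln G ± s) = G·exp(±s). The same limits come from 10^(mean_log10 ± sd_log10).
- Limits as defined in the SAP: exp(k·ln G ± k·s) = [G·exp(±s)]^0.4343.

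A limit is therefore right only if its correct value is exactly 1 µg/mL. Both limits cannot equal 1 when s > 0, so every bar with non-zero SD is wrong under the literal definitions.

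**When the bar excludes its point.** The literal bar contains G only if |k·ln G − ln G| ≤ k·s. That is |ln G| ≤ [k/(1 − k)]·s = (0.4343/0.5657)·s = 0.7677·s.

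**Size, with assumed log10 SD 0.2** (10^±0.2 = 0.631 and 1.585):

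| G (µg/mL) | Correct bar | Bar as defined, exp(log10 G ± 0.2) | Contains G? |
|---|---|---|---|
| 0.5 | 0.32 to 0.79 | 0.61 to 0.90 | no |
| 1 | 0.63 to 1.58 | 0.82 to 1.22 | yes, but too narrow |
| 10 | 6.3 to 15.8 | 2.2 to 3.3 | no |
| 50 | 31.5 to 79.2 | 4.5 to 6.7 | no |

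**Check from raw values.** Take three assumed concentrations: 20, 35 and 50 µg/mL. G is 32.7. Natural logs with Exp() and log10 with 10^ both give 20.6 to 51.9. The literal rule gives exp(1.515 ± 0.201) = 3.72 to 5.56.

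**Range of G for which the literal bar contains its point**, with s = √ln(1 + CV²):

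- CV 30%: 0.80 to 1.25 µg/mL
- CV 50%: 0.70 to 1.44
- CV 100%: 0.53 to 1.90
- CV 200%: 0.38 to 2.65

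**Illustration only.** A one-compartment, first-dose calculation was run with these assumptions: one sixth of the dose per antibody, volume 40 to 100 mL/kg, half-life 1 to 7 days, CV 30% to 100%, doses 4 to 15 mg/kg, scheduled sampling times. Between 0 and 5 of 46 plotted points fell inside their own bar. The only half-life in the documents is from monkeys (Protocol 3.2.3: "ranging from 1 to 3 days over the dose levels tested"), so this shows a range and is not a prediction.

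**Where there is no bar.**

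- A cohort of one patient has no SD. Protocol 3.2.4.1 reports "1 patient each at 1 mg/kg and 2 mg/kg weekly (Q1W), 4 patients at 4 mg/kg Q1W", so as of Amendment 6 the two lowest weekly groups have none.
- Where more than half the values are below quantification, SAP 4.10.4.2 sets both the SD and the geometric mean to not determined.

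**The case against.** The strongest reply is that this is a wording slip with an obvious intent. The function is Exp(), both variables carry the suffix `_Ln`, and the geometric CV formula in SAP 4.10.4.3 is valid only for a natural-log SD. A programmer guided by these would draw correct bars. SAP 4.1 requires independent checking of all figures, and a bar detached from its point would be easy to see. The figures are descriptive and no decision rule uses them.

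Most of this stands, and it limits the weight of the point: harm follows only if the definitions are coded as written. It does not remove the contradiction. A check made against the SAP text could pass the literal version. Detachment would also not show if the plotted point were computed on the same basis, which the SAP leaves open. A true geometric mean of 10 would then plot at exp(1) = 2.7, inside its 2.2 to 3.3 bar, with both wrong.

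A reader might infer three stronger things, which the documents do not support:

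- *Most bars would miss their own points.* This needs concentrations, and a rule for computing the plotted point, that the documents do not give.
- *Every dose and time point is affected.* Single-patient cohorts and time points mostly below quantification have no bar.
- *The geometric CVs are wrong too.* SAP 4.10.4.3 names no base there, and its formula is the natural-log form. Naming the base would be prudent, but no error is stated.

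**Conclusion.** The point holds as an internal contradiction in an operative formula. Under the written definitions, every bar with non-zero SD in Figures 14.2.15 and 14.2.17 is wrong. Its limits are the correct ones to the power 0.4343, so on a log axis the bar has 43% of its proper length and is pulled toward 1 µg/mL. That result is algebraic and depends on no assumed concentration.

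Two things are conditional. Whether the figures come out wrong depends on the definitions being coded literally. Whether a bar excludes its point depends on the true geometric mean being plotted and lying away from 1 µg/mL.

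The direct reach is the error bars of two descriptive figures. Concentration tables, arithmetic-mean figures, individual profiles, PK parameters and the DLT analysis are untouched. It should be corrected before the figures are produced, but it does not bear on the trial's main conclusions.

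**What to change.** In SAP 4.10.4.1, replace log base 10 with natural log in both definitions (`sd_Ln` and `mean_Ln`) and keep Exp(). This agrees with the variable names and with the geometric CV formula in 4.10.4.3. Alternatively, keep log10, replace Exp() with 10^(mean ± SD), and rename the variables. Both give identical bars.

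The cost is an edit in two places for the first option, or to the formula and names for the second. No data, analysis set or other output changes. If the figures have already been programmed, confirm which base the code uses for the bars and for the plotted points.

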4.10.4.2 Handling of Values Below the Limit of Quantification (BLQ)

Handling of values below the limit of quantification (BLQ) and missing data in listings and for the calculation of descriptive statistics at each time point:

- At a time point where less than or equal to 50% of the values are BLQ, all BLQ values will be set to the $\frac{1}{2}^*$ lower limit of quantification (LLOQ), and all descriptive statistics will be calculated.
- At a time point where more than 50% of the values are BLQ, the mean, SD, geometric mean and CV% will be set to Not Determined (ND). The max value will be reported from the individual data, and the min and median will be set to BLQ.
- If all values are BLQ at a time point, no descriptive statistics will be calculated for that time point. Not Applicable (NA) will be written in the field for SD and CV% and BLQ will be written in fields for mean, geometric mean, min, median, and max.
- The number of BLQ values (n below LLOQ) will be reported for each time point.

4.10.4.3 Pharmacokinetic Parameters

Pharmacokinetic parameters for the first and second PK profile (as defined in 4.10.4.1) for each patient and each monoclonal antibody will be derived by model-independent, non-compartmental analysis (NCA) according to Symphogen's local procedures.

All derived serum PK parameters will be listed by mAb, dose schedule, dose group, patient, and actual time point (Listing 16.2.6.2.1-2) and summarized descriptively by mAb, dose schedule and group and day (Table 14.2.2.1-2). The following descriptive statistics will be presented for PK parameters: n, arithmetic mean, SD, geometric mean, geometric CV% (calculated as: $gCV\% = \text{SQRT}(\exp(s^2) - 1) * 100$; where s is the standard deviation of the log-transformed values), median, minimum and maximum values.

4.10.4.4 Pharmacokinetic Analysis

Descriptive statistics of serum concentrations will be reported with the same precision as the source data and serum concentrations.

PAREXEL International
Statistical Analysis Plan Template for Early Phase Studies

Symphogen A/S
 Sym013-01

In addition to general continuous summary statistics presented in section 4.2, for PK parameters, geometric means with coefficient of variation (CV %) will be also summarized.

For drug concentrations and concentration-dependent pharmacokinetic parameters, the rules of data presentation are described in table below.

Presentation of PK Parameters and Summary Statistics

Typical Variable	N	Digit rule	Minimum	Mean	Geometric		CV (%)
			/Maximum	Median	SD	Mean	
concentration	X	Significant digits	3	4	4	3	3
C _{max}	X	Significant digits	3	4	4	4	4
t _{max} *	X	Fixed decimal places	as raw data	as raw data	-	-	-
λ _z	X	Significant digits	4	3	5	5	5
t _{1/2}	X	Significant digits	3	3	4	4	4
AUC _(0-xx)	X	Significant digits	3	3	4	4	4
AUC _(0-τ)	X	Significant digits	3	3	4	4	4

* Mean and SD, geometric mean and CV will not be calculated for t_{max}.

4.11 Safety Evaluation

All safety summaries will be based upon the FAS as defined in Section 4.5.

4.11.1 The DLT Analysis Set will be used for evaluation of DLTs Dose Limiting Toxicities (DLT)

All DLT events will be listed. Presence and absence of DLTs will be presented by regimen and dose in the order of date of first dose.

PAREXEL International
Statistical Analysis Plan Template for Early Phase Studies

Symphogen A/S
Sym013-01

4.11.2 Adverse Events

The AEs will be coded using Medical Dictionary for Regulatory Activities (MedDRA) version 19.1.

TEAEs will be presented by MedDRA System Organ Class (SOC) and Preferred Term (PT). In all AE summary tables, SOCs and PTs will be presented in the order of descending frequencies as detailed in section 4.2. AE frequency accounts for number and percent of patients who have a specific SOC and PT as well as the worst grade, if there were multiple occurrences at different toxicity grade, which was determined using CTCAE v4.03.

For purposes of the summary tables, AEs will be classified as either being related to study drug or not related. AEs related to study drug will include AEs classified as 'Related', 'Probably Related' or 'Possibly Related'. AEs not related to study drug will include AEs that are 'Unlikely Related' or 'Not Related'.

All AEs will be listed. The AEs will be presented using summary tables including:

- Patient Overall Summary of TEAEs. This table will include following summaries:
 - Any TEAEs
 - Any related TEAEs
 - Any Serious TEAEs
 - Any related Serious TEAEs
 - Grade 3 or higher TEAEs
 - Any Related Grade 3 or higher TEAEs
 - Any TEAEs leading to Permanent Discontinuation of IMP
 - Any Related TEAEs leading to Permanent Discontinuation of IMP
 - Any TEAEs leading to interruption or Stop of study drug
 - Any Related TEAEs leading to interruption or Stop of study drug

PAREXEL International
Statistical Analysis Plan Template for Early Phase Studies

Symphogen A/S
Sym013-01

- Any TEAEs with an outcome of reduction or delay of study drug
- Any Relate TEAEs with an outcome of reduction or delay of study drug
- Any FATAL TEAEs
 - Fatal TEAEs within 30 days from last IMP infusion
 - Fatal TEAEs beyond 30 days from last IMP infusion
- TEAEs by Dose Group, SOC and PT
- Related TEAEs by Dose Group, SOC and PT
- TEAEs by Dose Group, SOC and PT and Worst CTCAE Grade
- Related TEAEs by Dose Group, SOC and PT and Worst CTCAE Grade
- Serious TEAEs by Dose Group, SOC and PT
- Related Serious TEAEs by Dose Group, SOC and PT
- TEAEs Leading to Withdrawal from Treatment by Dose Group, SOC and PT
- Related TEAEs Leading to Withdrawal from Treatment by Dose Group, SOC and PT
- Serious Adverse Events - Key Patient Information (non TEAEs will be flagged)
- Adverse Events with Outcome of Death - Key Patient Information (non TEAEs will be flagged)
- Adverse Events Leading to Discontinuation of Investigational Product - Key Patient Information
- Adverse Events Leading to Dose Reduction - Key Patient Information
- Adverse Events Leading to Dose Interruption- Key Patient Information
- Adverse Events Leading to Dose Stopped - Key Patient Information

PAREXEL International
Statistical Analysis Plan Template for Early Phase Studies

Symphogen A/S
Sym013-01

- Listing of Death (Deaths occurring within 30 days from last infusion of IMP will be flagged.) (non TEAEs will be flagged)

